Study Title: The Emmetropization Via Accommodation (EVA) Study

NCT Number: NCT03669146

Document Date: January 6, 2024

Emmetropization Via Accommodation (EVA) Study

I. Objective. The objective of this study is to determine if wearing a moderate spectacle under-correction (3.00D) and performing activities designed to stimulate accurate accommodation during a 15-month period will enhance emmetropization in highly hyperopic ($\geq +5.00D$) 3-month old infants. Our hypothesis is that more active and accurate accommodation, promoted with spectacle under-correction and accommodative exercises, will increase the rate of axial elongation to reduce hyperopia. The prediction is that the eye will modulate axial length by modifying ocular shape, that more accurate accommodation will be associated with creating a less oblate, more prolate eye shape that accentuates elongation. The results of this study would be clinically relevant almost immediately. Results from the proposed study would represent evidence-based guidelines for effective infant refractive care.

II. Background and Rationale. Most healthy human infants are born hyperopic, or farsighted (Mayer, Hansen, Moore, et al., 2001). The average cycloplegic refractive error for infants at birth ranges from +1.00D to +2.50D with standard deviations ranging from 1.50D to 2.50D (Cook and Glasscock, 1951; Luyckx, 1966; Mayer et al., 2001; Santonastaso, 1930; Wood, Hodi and Morgan, 1995; Zonis and Miller, 1974). Infants undergo a process called emmetropization in which their normal early hyperopic refractive error decreases over time by coordination of the development of optical power and axial length of the eye.

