Infants with refractive errors from $+5.00\text{D}$ up to $+7.00\text{D}$ who are randomized to standard therapy will receive no correction. Follow-up will occur on the same schedule as infants randomized to treatment: 1.5 months after the baseline examination and then every 3 months until completion at 18 months of age (6 follow-up visits after the baseline exam). Regular clinical care, if any is needed, will begin at the conclusion of follow up at 18 months. Infants in either the treatment or control group who have not achieved a refractive error of $<+3.50\text{D}$ in each eye by 18 months of age will be referred outside the study for an independent evaluation. This level of hyperopia is selected for referral at 18 months because of its association with an elevated level of risk for strabismus (Atkinson, Braddick, Robier, et al., 1996)

- iv. **Case Series Group.** Infants with a refractive error of $\geq+7.00\text{D}$ will receive treatment (same protocol as infants randomized to the treatment group of this study). The follow-up of the infants in this case series group is the same for those who are randomized to treatment.
- c. **Measurements.** The subject will be examined while seated in the parent's lap for all tests.
 - i. **Visual Acuity.** Preferential looking visual acuity with **Teller acuity cards** will be used to determine visual acuity without refractive correction. The Teller acuity cards will be presented at 55cm. The subject is observed through a center peephole of the acuity cards for preferential looking. Successively smaller patterns are presented until the subject either no longer displays preferential looking, or loses interest. Testing will be first be attempted monocularly but if the subject is resistant to occlusion, testing will be done binocularly. Final results are recorded in the subject's chart as the cycles/degree of the last card at which a response is noted in each eye.
 - ii. **Pupil testing.** Pupillary function is tested with a penlight for size, equality, shape, response to direct light, and consensual response.

- iii. **Version testing.** Versions are tested, with the examiner looking for any restrictions of yoked eye movements as the baby looks in different fields of gaze.

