There is no universally accepted outcome measure for infant accommodative response, therefore the analysis in this phase will be somewhat exploratory. The simplest metric to calculate would be the average accommodative response. However, variability in that response provides a useful perspective that distinguishes the infant with stable accommodation from the one that is less well-controlled or exhibits more of a searching accommodative behavior. Variability will be added as a covariate in analyses of the accommodative response. The simple standard deviation in accommodation is one measure of this variability. Another approach would be to look for periodic variability through Fourier analysis of the response. This analysis would be exploratory. Analyses are typically of 10 second segments of response. If infants are too unsteady to give such lengths of uninterrupted data, then the analysis may not be feasible. If the analysis can be done, then power at low, mid, and high temporal frequencies will be used as covariates in the analyses of accommodative response. Other potential metrics might be lag-minutes or diopter-minutes, essentially area-under-the-curve summary measures of diopters of lag, or alternatively, diopters of accommodative response per minute of recording.

- vi. **Cycloplegic refractive error** will be measured at all visits. Refractive error will be measured by **cycloplegic retinoscopy** by a masked examiner (primary outcome of the treatment phase of the study). The parents of the subject will be instructed not to discuss the treatment group the patient is in to the masked examiner. Measurements will occur 30 minutes after drop instillation. One drop of proparacaine 0.5% will be instilled in each eye, followed by two drops of cycloplegic agents. The drops used for cycloplegia are the following:
 - 1. Tropicamide (1%) will be used only at the screening visit
 - 2. Cyclopentolate (1%) will be used during all remaining visitsThe neutral point for the horizontal meridian is recorded first, then the neutral point for the vertical meridian. If the axes are oblique, the true meridian is measured by projecting the retinoscopy beam on to a protractor on the wall. **SureSight autorefraction** will be also be performed on both eyes from 35cm by the investigator (unmasked).

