The basic analysis will be a two-sample t-test comparison of the change in refractive error between the two groups at 9 months and again at 18 months of age. Analysis of Covariance (ANCOVA) will be used to compare the change in refractive error between the two treatment groups adjusting for any possible confounding variables. Refractive error at 3 months along with any other identified confounders will be included as covariates in the analysis. Randomization of infants into the two treatment groups should protect against confounding, however, testing will be performed and adjustments made for imbalances in confounders between groups.

The relationship of accommodative effort and accommodative lag with change in refractive error between 3 and 9, or 3 and 18 months will be analyzed by repeated measures analysis of variance. We will fit a linear functions describing the relationship between change in refractive error and accommodation as the repeated factor, either effort or lag. A significant effect for type of accommodation will indicate that the greater slope is the better explanation of the driving force for change in refractive error.

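### The accommodation analysis names no term for randomised arm or 3-month refraction, so with readings taken after treatment starts the arm difference alone can produce the slope it interprets

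*Combined protocol and SAP*

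**What the plan says.** The accommodation paragraph of section F covers "The relationship of accommodative effort and accommodative lag with change in refractive error between 3 and 9, or 3 and 18 months". The method is repeated measures analysis of variance, with linear functions "describing the relationship between change in refractive error and accommodation as the repeated factor, either effort or lag". The decision rule is: "A significant effect for type of accommodation will indicate that the greater slope is the better explanation of the driving force".

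The paragraph before it describes a different analysis, the ANCOVA comparing the two groups. There the plan says: "Refractive error at 3 months along with any other identified confounders will be included as covariates in the analysis". Nothing carries that sentence over to the accommodation model. The only covariates named for accommodation analyses are in section D.c.v (Accommodative response and lag): "Variability will be added as a covariate in analyses of the accommodative response", with Fourier power added if that analysis proves feasible. The same section sets the status of the work: "There is no universally accepted outcome measure for infant accommodative response, therefore the analysis in this phase will be somewhat exploratory".

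Three other places bear on the point:

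- Section I (Objective) makes treatment an intended cause of both variables: "more active and accurate accommodation, promoted with spectacle under-correction and accommodative exercises, will increase the rate of axial elongation to reduce hyperopia".
- The measurement schedule (section D.d) has accommodation measured at every visit from baseline to 18 months. Section F does not say which visit's reading enters the model.
- Section D.b.iv says that case-series infants "will receive treatment (same protocol as infants randomized to the treatment group of this study". Section F does not say whether they enter the accommodation model.

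**The concern.** When treatment moves two variables, pooling the arms makes those variables correlate even if they are unrelated inside each arm. Here the two variables are accommodation and refractive change, and the plan attaches a causal reading to the slope between them. Followed literally, the analysis could credit accommodation with driving emmetropization when all it had detected was that treated and control infants differ on both measures.

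Starting refraction is a second route. Figure 1 in section II presents change in hyperopia as a function of hyperopia at 3 months. If accommodation also varies with starting hyperopia, the two will be associated for that reason.

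This is the only planned analysis that links accommodation to refractive change, so an accommodation claim in the report would rest on it.

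**Working it through.** **The plan's own figures.** The documents give no sample size, power or effect size for the accommodation analysis. The inputs below come from the sample-size paragraph for the main comparison: 13 per group, difference 1.75D, SD of change 1.50D. The usual two-mean formula gives 2 × (1.50 × (1.960 + 1.282) / 1.75)² = 15.44, so 16 per group. The plan reaches 13 through a repeated-measures adaptation whose correlation is not stated, so 13 cannot be confirmed. It serves here only as the planned number of completers (13 / 0.9 = 14.4, so 15 enrolled per arm and 30 in all).

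**Assumptions.** The shift d in accommodation between arms, in within-arm SDs, is not in the documents; 0 to 2 is shown. There is one reading per infant, normal errors, and no link between accommodation and change inside either arm. Change is scored as reduction in hyperopia.

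**Single slope, post-treatment readings.** With a = 1.75 / (2 × 1.50) = 0.583 and c = d / 2, the pooled correlation is r = ac / √((1 + a²)(1 + c²)). For d = 1 this is 0.583 × 0.5 / √(1.340 × 1.25) = 0.225. False-positive rates at two-sided 0.05, from 100,000 simulated trials per row:

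| Shift d (SD) | r from formula | Without arm term | With arm term |
|---|---|---|---|
| 0 | 0 | 5.0% | 5.1% |
| 0.5 | 0.12 | 9.4% | 5.0% |
| 1 | 0.23 | 20.5% | 5.0% |
| 1.5 | 0.30 | 34.3% | 4.9% |
| 2 | 0.36 | 46.9% | 5.0% |

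Shorter simulations of the last row without an arm term gave 46% to 49%. If treatment does not change refraction, the rate stays near 5% at every shift, so both arm effects are needed.

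**Effort-versus-lag contrast.** This is the comparison that the decision rule uses. It was tested as a difference between two dependent correlations, with independent noise in effort and lag and shifts of 0.5 / 1 / 1.5 / 2 SD:

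- Both measures move by the same amount and slopes are compared by size: about 5% throughout.
- Only effort moves: 7% / 12% / 19% / 25%.
- Effort rises, lag falls, and slopes are compared with sign: 13% / 31% / 48% / 60%.

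In a joint regression on effort and lag, the last case gives 12.7% / 31.6% / 47.0% / 58.6%. With an arm term it returns to 4.8% to 5.3%.

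**Baseline reading only.** Randomisation makes a 3-month reading independent of arm, so omitting arm does not bias the slope. The treatment effect goes into the error term instead: 1.50² + (1.75 / 2)² = 2.25 + 0.77 = 3.02, and 3.02 / 2.25 = 1.34, a 34% rise in residual variance.

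**Starting refraction alone.** Assume no arm effect, 3-month refraction uniform from 5 to 7D, change rising 0.5 to 1.0D per dioptre, residual SD 1.4D, and a correlation of 0.3 to 0.7 between accommodation and starting refraction. The slope is falsely significant in 5.3% to 25.7% of trials without a 3-month refraction term and in 4.4% to 5.3% with one.

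**Power cost of the arm term.** Suppose instead that accommodation carries the whole 1.75D. The slope is then 1.75 / d and the residual SD is √(2.25 − (1.75 / d)²). Pooled against arm-adjusted power is 1.00 against 1.00 at 1.5 SD, 0.99 against 0.89 at 2 SD, 0.97 against 0.68 at 2.5 SD, and about 0.95 against 0.50 at 3 SD.

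**The case against.** The plan itself calls the accommodation work somewhat exploratory, and the masked retinoscopy comparison between arms does not depend on it. That limits the severity. It does not remove the problem, because the decision rule is worded as an explanation and not as an association.

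The paragraph is silent on arm and 3-month refraction; it does not exclude them. An analyst might add both. A plan should not leave that to chance when it names 3-month refraction for the neighbouring ANCOVA.

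Accommodation is measured with no correction worn, so the spectacles do not shift the reading directly. This stands. An arm difference would have to come from the intended change in accommodation or from reduced hyperopia. The second possibility also allows reverse causation, which an arm term does not resolve.

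The strongest objection is that adjusting for arm sets aside the randomised contrast through which the hypothesis is meant to work. The power figures bear this out at large shifts. An arm-adjusted slope should therefore not be the only evidence reported.

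A reader might go further in three ways that the documents do not support:

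- That this is the study's only test of mechanism. Section F also plans a test of ocular shape, through relative peripheral refraction by arm.
- That refractive change and accommodation type are the model's only terms. Section D.c.v adds response variability, although that does not address arm.
- That the case series will be pooled with the randomised infants. Nothing says so, and the sample-size paragraph counts it separately.

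**Conclusion.** The concern holds, with conditions. As written, the accommodation model lacks the two terms needed to keep the arm difference and starting refraction out of the slope. If post-treatment readings are used, and treatment shifts both accommodation and refraction as the study hypothesises, a single pooled slope is falsely significant in about 9% to 47% of trials for assumed shifts of 0.5 to 2 SD. For the contrast that the plan interprets, the rate can be anywhere from about 5% to about 60%. The plan does not settle where in that range it falls, because it states neither the visit nor whether slopes are compared by size or with sign. If only the 3-month reading is used, the arm problem reduces to a 34% larger residual variance, while starting refraction can still confound.

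These rates rest on one reading per infant, whereas the plan uses both eyes and controls for within-infant correlation. That control supplies neither missing term. The point should be corrected in the analysis plan, but it is no threat to the primary result.

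**What to change.** In the accommodation paragraph of section F:

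1. State which visit or visits supply the accommodation reading, and whether the effort and lag slopes are compared by size or with sign.
2. Add randomised arm and 3-month refraction as terms, alongside the variability covariate already named.
3. Fit the model in the randomised infants and show the case series separately and descriptively.
4. Replace the decision rule. Report the arm-adjusted slope as the main association, report the between-arm (mediation) part separately, and do not call accommodation the driving force on the pooled slope alone.

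The cost is wording, two degrees of freedom, and some loss of power for the arm-adjusted slope if treatment shifts accommodation by about 2 SD or more. Both added variables are already collected, so no new data are needed.

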Sample size calculations were performed using the formula adapted by Lindsey to take advantage of the power gained from obtaining repeated measurements across time and eyes (Lindsey, 2001). Data from the Berkeley Infant Biometry Study (BIBS) were used to obtain an estimate of the within-subject/within-visit repeatability of refractive error and the correlation of these measurements across time. The standard deviation for change in refractive error from 3 to 9 months of age from infants with hyperopia $>+5.00\text{D}$ enrolled in BIBS was 1.17D. Data from Atkinson et al. suggests a standard deviation of 1.50D and Ingram et al. give a standard deviation for change is assumed to be 1.36D (Atkinson et al., 2000; Ingram et al., 2000). To provide the most conservative estimate of sample size, the standard deviation of change is assumed to be 1.50D. If a new, difficult, expensive treatment strategy is to be adopted, the benefit must be substantial. The ordinary decrease in hyperopia in uncorrected, highly hyperopic infants might be 1.2D to 1.34D (Atkinson et al., 2000; Ingram et al., 2000). We would expect that there would be little enthusiasm for this new approach if the decrease in hyperopia in treated infants was not on the order of 3.00D (an improvement compared to controls of 1.75D). Using these parameters, a sample size of 13 in each randomized group will be needed ($\alpha=0.05$, $\beta=0.1$, two-sided test). If we estimate that 10% of the infants may not complete the follow up, 30 infants need to be enrolled with 15 randomly assigned to each of the two randomized groups. The rather large difference relative to its standard deviation to be detected ($1.75/1.50 = 1.17$) along with the increase in power obtained by taking repeated refractive error measurements help to keep the sample size low. However, given the prevalence of high hyperopia (more than $+5.00\text{D}$) in the population of 3 months old infants, a sample size of 30 eligible infants (for randomization, not including the case series) is not trivial. Up to 10 eligible infants will be enrolled in the case series portion of the study. One of the major efforts in this project will be screening the 900 infants needed to find those that are eligible.

C. Measurement/Instrumentation

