- iv. **Binocularity testing.** The examiner will determine if strabismus is present using a unilateral cover tests as well as Hirschberg evaluation. Subjects with an existing strabismus are not eligible. Subjects who develop a strabismus during the study period will be referred for further evaluation and retained for follow up.
- v. **Accommodative response and lag** will be measured with the Schaeffel PowerRefactor and by dynamic retinoscopy with no refractive correction worn.

The Schaeffel PowerRefactor is an infrared, binocular photorefractometer capable of measuring the meridional refractive error, and therefore the dynamic accommodative response, of both eyes simultaneously at 25 Hz. Photorefraction in general and this instrument specifically have been shown to compare well to conventional retinoscopic measures of accommodation with the added advantage of measuring accommodative response and its variability in both eyes over a more extended period of time (Blade and Candy, 2006; Braddick, Atkinson, French, et al., 1979; Howland, Dobson and Sayles, 1987; Rosenfield, Portello, Blustein, et al., 1996; Seidemann and Schaeffel, 2003). The PI's experience with this instrument is that maintaining attention is critical to the validity of measurements. Inattention and the drifting of gaze from central fixation on the accommodative target interfered with the comparability of measurements to conventional dynamic retinoscopy (Gabriel and Mutti, 2009). To filter out readings that might be obtained when fixation is poor, the "Gaze Control" setting on the PowerRefactor will be set to 15° in "Binocular" refraction mode.

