The accommodative targets are a set of plush stuffed toys. The texture of the toy maintains a range of spatial frequencies available to the baby that scale with fixation distance to drive the accommodative response. Such targets have been used successfully by the PI and another laboratory in studies of infant accommodation (Blade et al., 2006). A large circular "hot" infrared reflecting mirror is positioned at 45° in front of the infant. The reflecting mirror allows the accommodative target to be positioned in real space in front of the infant along the line of sight and coincident with the axis of the photorefractor. This avoids problems with fixation drifting from the 15° limit set on the machine. The PowerRefactor is placed on an instrument table 1 meter away from the subject on the other side of the mirror. The proximity of the mirror to the infant means that only a maximum of 4D of accommodation can be stimulated. Readings will be taken for approximately one minute at each of two distances: **6 meters and 0.33 meters**. Filtering of the data will remove blink artifacts or non-physiologically rapid changes in accommodative response (>10D/sec) (Harb, Thorn and Troilo, 2006).

Dynamic Retinoscopy will be assessed like a modified monocular estimation method (MEM), which is commonly used in clinical practice. Dynamic retinoscopy has been found to be similar to objective accommodative measurements, which we are measuring with the

PowerRefractor (Gabriel et al., 2009). Dynamic retinoscopy would be more directly applicable to clinicians who see patients regularly and do not have access to an instrument that can measure accommodation objectively in a clinical setting. Measurements will be obtained at **0.33 meters**.

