5. Compliance with visual engagement and vision therapy exercises. Parents will out a form at each follow up visit listing how compliant they were with performing accommodative therapy with the subject. Parents of the subjects will list how many minutes they were able to engage in the recommended visual activity each day. Parents will be given a pre-printed calendar to help them keep track of compliance on a daily basis. This will be turned in to the investigator at the next follow up.

xi. Ocular health. The ocular health will be assessed at the baseline examination and at the final visit with a direct ophthalmoscope, transilluminator with a 20 Diopter condensing lens, or binocular indirect ophthalmoscope.

d. Measurement and Visit Schedule

Measurement	S	V1/B	V2	V3	V4	V5	V6	V7
Target Age (months)	2	3	4.5	6	9	12	15	18
Cycloplegic refractive error w/ SureSight	X		X	X	X	X	X	X
Cycloplegic refractive error w/ Retinoscopy	X	X	M	M	M	M	M	M
Peripheral Refractive error w/ Sure Sight		X			X			X
Accommodative response and lag w/ Power Refractor		X	X	X	X	X	X	X

Accommodative response and lag w/ MEM		X	X	X	X	X	X	X
Ocular Health		X						X
Ocular Motility		X	X	X	X	X	X	X
Ocular Alignment		X	X	X	X	X	X	X

LEGEND: S = Screening visit at Pediatrician's office

V1/B = Baseline Examination

V2 = Visit 2, 4.5 months of age

V4 = Visit 4, 9 months of age

V6 = Visit 6, 15 months of age

M = Performed by an examiner

V3 = Visit 3, 6 months of age

V5 = Visit 5, 12 months of age

V7 = Visit 7, 18 months of age

M = Performed by an examiner masked to the infant's group assignment

e. **Visit Schedule.** The target and acceptable dates for each study visit are given below. If a monthly examination cannot be completed within the acceptable range, that visit will be considered as missed. It will be important to stress to parents at enrollment the importance of attending each of these scheduled visits. The acceptable range for the 6 and 18 month examinations has been extended to 14 days after the target date to maximize the probability that this examination can be completed.

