f. **Development of Strabismus.** The subject population of this study is at risk for developing strabismus (Anker et al., 2004; Cotter, 2007; Pascual et al., 2014). This will be discussed with the parents of potential subjects during screenings and during the consent process prior to the baseline examination. If a subject develops a strabismus, the subject will be discontinued from treatment in the study. The subject cannot remain in either arm of the study because of the different standard of care in prescribing philosophy that occurs with the development of strabismus (typically providing a full refractive correction for hyperopia). The subject will remain in the study and will continue to be followed for observation of all study measurements and outcomes. The subject's parents will have the option of their child remaining under the care of [name] in the Ohio State University College of Optometry Pediatric clinic, or any other doctor within the Ohio State University College of Optometry, or seek or be referred to another provider for a second opinion or for patient care. Any visits or treatment of strabismus or any clinical sequelae of the strabismus would be at the discretion of the licensed eye care provider and separate from the study. Follow up visits related to the study will follow the same schedule and contain the same measurements listed in the protocol.

E. **Internal Validity.** There are no threats to internal validity. All procedures performed in the examination are standard procedures that have been performed frequently in other studies. Threats to external validity might be present in selection bias. The sample of patients to be recruited will be identified at Riverside Pediatrics Associates by screenings of age appropriate infants. The screenings will be performed by [name], [name], or a nurse that has been adequately trained. The age, gender, and ethnicity of these patients might not be a true representation of the general population of full term, healthy infants.

F. **Data Analysis.** All data analysis will be performed using SPSS (Version 24). Statistical significance will be assessed using two-sided tests with an alpha level of 0.05. Data from both eyes will be included in all analyses and techniques to control for intra-subject correlations will be used.

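### Section F (Data Analysis): a significant effect for type of accommodation does not make the steeper slope the better explanation of refractive change (minor)

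*Combined protocol and SAP*

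**What the plan says.** Section F relates accommodative effort and accommodative lag to change in refractive error (3 to 9 or 3 to 18 months) by repeated measures analysis of variance. It fits linear functions with "accommodation as the repeated factor, either effort or lag", and then applies the rule: "A significant effect for type of accommodation will indicate that the greater slope is the better explanation of the driving force". It defines neither effort nor lag for this purpose, and it names no visit, instrument, distance, covariate or sign convention.

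The measurement sections leave several candidates:

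- Section D.c.v says that response and lag "will be measured with the Schaeffel PowerRefactor and by dynamic retinoscopy with no refractive correction worn".
- For the PowerRefractor, "Readings will be taken for approximately one minute at each of two distances", namely 6 m and 0.33 m. Dynamic retinoscopy is done at 0.33 m.
- The schedule in section D.d lists "Accommodative response and lag w/ Power Refractor", and the same by MEM, at all seven visits from V1 to V7.
- Section D.c.v says no outcome measure for infant accommodation is universally accepted, "therefore the analysis in this phase will be somewhat exploratory". It adds response variability as a covariate and mentions lag-minutes and diopter-minutes as possible metrics.

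Section F also says that both eyes enter all analyses and that "techniques to control for intra-subject correlations will be used".

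**The concern.** The rule moves from a significance test to a statement about mechanism, and neither step is sound. A larger raw slope is not a better explanation, and an effect for type need not be a test of slopes at all. The phrase driving force is also causal, whereas effort and lag are observed and are not randomised separately. The intervention is meant to make accommodation both more active and more accurate.

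At stake is the secondary account of how treatment works. This is the only analysis in section F that links accommodation to refractive change, and the Objective's hypothesis runs through accommodation. A published statement that effort, or lag, is the driver could rest on the scale of a measure or on an algebraic identity.

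**Working it through.** The plan gives no figure for this rule, so there is none to reproduce. The check is algebra followed by illustrations.

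**1. Slope against strength of association.** The slope of change y on measure x is b = r × SD(y)/SD(x), and the variance explained is r². With SD(y) = 1.50D from the sample size paragraph, and assumed SDs and correlations for the two measures:

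- Equal strength (r = 0.5 each), SDs 0.5D and 1.5D: b = 0.5 × 1.5/0.5 = 1.5 and 0.5 × 1.5/1.5 = 0.5. With 26 infants and a correlation of 0.5 between the measures, the slope difference was significant in 57% of simulated trials, always favouring the less variable measure.
- Weaker predictor steeper: r = 0.4, SD 0.5D gives b = 1.2; r = 0.6, SD 1.5D gives b = 0.6. The difference was significant in about 26% of trials, almost always favouring the weaker predictor.

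If one measure is in dioptres and the other in lag-minutes or diopter-minutes, the slopes are not on a common scale at all.

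**2. The algebraic link.** Assume lag = demand − response.

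- If effort means response to a fixed demand, then b(effort) = −b(lag), with identical R² and p-value. The signed difference is 2b, so testing it is the same as testing b = 0.
- If effort means total accommodation without correction at 0.33 m, then effort = H + 3 − lag, where H is hyperopia. The two measures now differ only through H.

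The link is weaker if effort and lag come from different instruments or distances, which section F does not settle.

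**3. Illustration under the second definition.** From the documents: 26 infants (13 per arm), SD of change 1.50D, hyperopia +5 to +7D, and an arm difference of 1.75D ("an improvement compared to controls of 1.75D"). Assumed: H uniform, so Var(H) = 2²/12 = 0.333; lag SD 1.0D; effort is the true driver with r = 0.5; arm in the model. With c = corr(H, lag), Var(effort) = 0.333 + 1 − 2c × 0.577.

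| c | SD(effort) | slope, effort (R²) | slope, lag (R²) |
|---|---|---|---|
| −0.3 | 1.296 | 0.58 (0.25) | −0.68 (0.20) |
| 0 | 1.155 | 0.65 (0.25) | −0.65 (0.19) |
| +0.3 | 0.993 | 0.75 (0.25) | −0.62 (0.17) |

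For c = −0.3, slope(effort) = 0.5 × 1.5/1.296 = 0.58 and slope(lag) = 0.58 × (−0.173 − 1)/1 = −0.68. The true driver explains more and has the shallower slope.

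The table shows the percentage of simulated trials (20,000 per setting) that were significant and named the wrong driver. The plan's wording allows change to be regressed on accommodation or the reverse; the less favourable direction is shown for each driver.

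| True driver, regression | Test | c = −0.3 | 0 | +0.3 |
|---|---|---|---|---|
| Effort, change on accommodation | signed | 61.8 | 41.8 | 17.5 |
| | absolute | 14.6 | 4.1 | 0.4 |
| Lag, accommodation on change | signed | 61.2 | 39.2 | 16.2 |
| | absolute | 11.0 | 2.5 | 0.3 |

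In the other two pairings the figures are 1–19% (signed) and at most 0.5% (absolute). For driver r from 0.3 to 0.7, the less favourable pairings span 10–84% (signed) and 0.2–24% (absolute). With nothing associated with change, the signed test rejects in about 5%.

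**4. Effect for type read as a main effect.** If change is the outcome, stacked by type, the mean difference is zero by construction. If accommodation is the outcome, the effect compares levels of effort and lag. With equal slopes and assumed means of 1D and 6D it was significant in 100% of trials, while the test of slope difference rejected in about 6%. Neither version compares slopes.

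**The case against.** The strongest case on the other side has five parts.

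- **Stakes.** The Objective does not set effort against lag, so its hypothesis does not need a winner, and treatment is tested by the randomised comparison. The protocol itself calls this work somewhat exploratory. This stands and sets the severity.
- **Intended test.** Because the rule speaks of the greater slope, a slope comparison is probably meant. That is fair, but the slope reading still fails by steps 1 and 2. The main-effect result also depends on coding: at an assumed mean lag of 4D, significance falls from about 66% to about 33% when change enters as an uncentred covariate. No single main-effect percentage should be attached to the plan.
- **Units.** If both measures are in dioptres, change per dioptre is interpretable, and R² depends on spread too. This stands. It means that standardised estimates or R² should not become a new rule for naming the driver.
- **Inputs.** Lag SD, driver strength and the lag-hyperopia correlation are all assumed. Eligibility needs +5.00D in only one eye, both eyes are analysed, and section F does not exclude the case series here. The percentages are illustrations only.
- **Replacement test.** A formal comparison of fit would have low power (about 9–12% in the step 3 setting, about 15% with 4–7D, about 27% with 36 infants at 5–9D). It would meet the same algebraic limits. This also stands, so no such test is recommended and no power figure should go into the plan.

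A reader might infer that the signed test is significant by construction, or that the wrong driver is always named. Neither follows: it rejects in about 5% when nothing is associated, and with absolute slopes errors can be rare.

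**Conclusion.** The rule is not a valid inference under any of the readings considered, and nothing elsewhere in the document repairs it. The slope-and-spread argument needs no assumed inputs. The link between effort and lag assumes that lag is demand minus response and that both come from the same recording. The frequency of a wrong conclusion cannot be fixed from the documents: the illustrations run from under 1% with absolute slopes to over 60% with a signed test.

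Severity is minor. A reader might infer that the trial's main result is undermined; the documents do not support that. The primary outcome is cycloplegic retinoscopy compared between randomised groups, and neither that comparison nor the sample size uses this rule.

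**What to change.** In section F:

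1. Delete the rule linking a type effect and the greater slope to the driving force.
2. State which visit, instrument and distance supply effort and lag, and how each is calculated.
3. Report the association of each with change in refractive error in separate models. Each model should include randomised arm, the two-eye correlation control that section F already promises, and the variability covariate of section D.c.v. Give standardised estimates with confidence intervals.
4. Word the result as association, and treat any comparison of fit as descriptive only.
5. State two limits. Effort and lag from the same baseline recording cannot be separated once 3-month refractive error is in the model: effort = H + 3 − lag, so with H included the two fits are identical. Effort at a follow-up visit, if defined as total accommodation, contains that visit's refractive error and hence part of the outcome, so a better fit there does not show a driver.

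The cost is one rewritten paragraph plus the definitions, with no new visits or measurements. The downside is that the trial gives up naming effort or lag as the driving force.
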